5.1.4 Demographic Information

The following demographic information will be collected at Screening: date of birth, gender, race, and ethnicity. If local regulations do not allow a full date of birth to be collected, the birth date will be reported to the extent allowed (eg, month and year or year only).

5.1.5 Physical Examination

Complete, age-appropriate physical examinations will be performed by the Investigator or qualified designee at the time points specified in the SOA. These examinations will include an assessment of the subject's general appearance; skin; head, eyes, ears, nose, throat and head circumference; heart; lungs; abdomen; extremities/joints; and neurological status. Abnormal findings will be recorded in the CRF.

5.1.6 Height and Weight

Height and weight will be measured at the time points specified in the SOA. Weight-for-age (WFA), weight-for-height (WFH), height-for-age (HFA), and body mass index (BMI)-for age will be derived during data analysis, and percentiles or z-scores will be determined for each of these derived parameters by standardization to age- and gender-appropriate CDC growth charts.

5.1.7 Vital Signs and Electrocardiogram

Vital signs, including pulse rate, respiratory rate, systolic and diastolic blood pressure (BP), and body temperature will be taken at the time points specified in the SOA. In addition, a baseline blood pressure measurement should be taken in triplicate prior to administration of SBC-103 at screening or prior to SBC-103 administration on either Day 0 in Part A or the subject's the next scheduled infusion. The baseline BP measurement should be done as follows:

- Ensure the subject is relaxed or distracted.
- Obtain 3 separate BP measurements.
 - The same arm should be used for each reading.
 - The right arm is preferred for these repeat BP measurements for consistency and comparison with standard tables and, because of the possibility of coarctation of the aorta, which might lead to false (low) readings in the left arm.

- \circ Each reading should be taken on the same day >15 minutes apart.
- The same suitable equipment should be used for each reading.
- Each measurement should be recorded in the subject's source records and in the CRF

On Day 1 in Part A, vital signs will be taken prior to hospital discharge. During dosing visits vital signs will be taken pre-dose (within approximately 30 minutes), approximately every 15 minutes during infusion and approximately every 15 minutes for 2 hours after completion of the infusion. Vital signs should also be obtained after the lumbar puncture is completed as per the standard of care. In Part B, the duration of post-infusion vital signs monitoring may be shortened to 1 hour starting with Week 54, provided that there is no occurrence of IARs during the infusion. In Part C, the duration of post-infusion vital signs monitoring may be shortened to 1 hour starting with Week 26 of Part C, provided that there is no occurrence of IARs during the infusion.

Every effort will be made to collect a 12-lead ECG during the time points specified in the SOA; 12-lead ECGs will be collected in triplicate during Part A of the study only. ECGs will be reviewed by the Investigator, or designee, and any abnormalities will be specified as clinically significant or not clinically significant.

Due to the behavioral issues typical of subjects with MPS IIIB, ECG assessments may not be able to be completed, but should be attempted whenever possible.

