3.1.3.1 Criteria for Dosing in Part C

The first subject who is eligible to dose escalate in Part C (see Section 4.3.4) and who is randomized to receive 5 mg/kg in Part C will be the first subject dosed in Part C; in the event that >1 subject is eligible at the same time, subjects will be dosed sequentially based on subject identification number (eg, Subject [Site #]-003 would be dosed before Subject [Site #]-005). As shown in Figure 3, the decision to continue dosing this subject and to start dosing the remaining 4 subjects at 5 mg/kg will be made by the Sponsor based on SRC recommendations after review of 24-hour safety data from the first subject dosed at 5 mg/kg. The remaining subjects randomized to the 5 mg/kg dose group may be dosed in parallel providing they meet all eligibility criteria to participate in Part C.

The decision to dose the first subject at 10 mg/kg will be made by the Sponsor based on SRC recommendations after review of safety data from 1 subject who completes the first 2 doses at 5 mg/kg, and review of all available safety data from any other subjects who have received at least 1 dose of SBC-103 at 5 mg/kg (Figure 3). Similar to initiation of dosing at the 5 mg/kg dose level, the first subject to receive the 10 mg/kg dose will be the first eligible subject to dose escalate in Part C who is randomized to the 10 mg/kg group; in the event that >1 subject is eligible at the same time, subjects will be dosed sequentially based on subject identification number. The decision to dose the remaining 5 subjects at 10 mg/kg will be made by the Sponsor based on SRC recommendations after review of 24-hour safety data from the first subject dosed at 10 mg/kg. The remaining subjects randomized to the 10 mg/kg dose group may be dosed in parallel providing they meet all eligibility criteria to dose escalate in Part C.

Intra-subject dose escalation from 5 to 10 mg/kg based on all available safety, PK, and PD/efficacy data may not occur without prior written approval from the Sponsor. Dose reductions may be considered for safety and tolerability at any time in Part C.

Page 49 of 121

Figure 3: Planned Subject Treatment and Dose Escalation Schedule in Part C (Therapy at 5 and/or 10 mg/kg)

Page 50 of 121

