3.3 Rationale for Dose and Escalation Timing

3.3.1 Rationale for Dose Escalation in Part A (Initial Therapy)

Considering the potential for immunogenicity with a protein product, evaluation of the safety and tolerability following multiple rather than single doses prior to escalation is important. Most clinical observations in nonclinical studies occurred by the fourth dose (see Section 1.3). Therefore, In Part A, the decision to escalate into the next dosing cohort (from Cohort 1 to Cohort 2 and from Cohort 2 to Cohort 3) will be made by the Sponsor, based on SRC recommendations after review of safety data from the first subject who completes the first 4 QOW doses in the dose cohort and 24-hour safety data from Subject 3 in the same dose cohort. Intra-patient dose escalation is not planned for Part A.

3.3.2 Rationale for Intra-Patient Dose Escalation in Part B (Therapy at 1 and/or 3 mg/kg)

Based on the experience with neurodegenerative diseases, it is anticipated that clinical response to treatment may not be observed sooner than 6 months after initiating treatment with SBC-103. Therefore, evaluation of safety and tolerability data as well as biomarker and response to treatment data will take place after 24 weeks of treatment in Part A. With the intent of treating patients with the lowest dose that is safe and tolerable and which has potential for efficacy, dose escalation may be proposed for individual subject(s) at any time in Part B as described in Section 3.1.2 and Section 6.1.

3.3.3 Rationale for Additional Dose Escalation in Part C (Therapy at 5 and/or 10 mg/kg)

Preliminary available clinical safety, PK, and PD data (see Section 1.4.1) from this study together with existing toxicokinetic and toxicology data from the juvenile Cynomolgus monkey study provide a safety margin (see Section 1.5.1.4) that supports dose escalation to 5 and 10 mg/kg in Part C. Given the available safety data from Parts A and B and the prior SBC-103 exposure in these patients, 24-hour safety data from 1 subject at each dose are considered appropriate to permit the expansion of each dose cohort, and data from 1 subject who completes the first 2 doses at 5 mg/kg is considered appropriate to initiate dosing at 10 mg/kg.

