In addition, ongoing safety and PD data from Part C will be reviewed on an ongoing basis to guide further dose selection (ie, escalation from 5 to 10 mg/kg or reduction from 10 to 5 mg/kg) in this study with the goal of treating patients at the lowest dose that is likely to demonstrate clinical benefit while also being safe and tolerable.

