7.1.3 Adverse Events of Special Interest (Infusion-Associated Reactions)

IARs will be considered AEs of special interest. Any AE that occurs during the infusion or within 4 hours after the infusion is completed and is assessed by the Investigator as at least possibly related to study drug will be designated as an IAR for this study. In addition, if, at any time during the study, the Investigator observes symptoms that he/she considers to be consistent with an IAR or hypersensitivity reaction related to administration of study drug, the symptoms should be recorded as an AE(s) and designated as an IAR(s). Individual adverse event terms should be recorded rather than the terms IAR or infusion associated reaction.

As with any ERT, medications and equipment for the treatment of hypersensitivity reactions must be available for immediate use in case of unexpected, severe hypersensitivity reaction. These supplies include, but are not limited to, oxygen, acetaminophen, antihistamines (eg, diphenhydramine, parenteral and oral), corticosteroids, epinephrine, and cardiopulmonary resuscitation devices.

General guidelines for classifying the severity of a reaction are provided in Section 7.1.1

For similar biological products, most acute IARs occur within 2 hours of the infusion. Signs of a possible acute IAR may include:

• Hyperemia (flushing), fever and/or chills, nausea, pruritus, urticaria, gastro-intestinal symptoms (vomiting, diarrhea, abdominal cramping), cardiopulmonary reactions, including chest pain, cardiac arrhythmias, dyspnea, wheezing, stridor, hypotension or hypertension.

General guidelines for the diagnosis and management of IARs are provided in Table 9. These guidelines are not intended to be comprehensive. The Investigator should use clinical judgement in the management of IARs in individual subjects participating in this study. In the case of a severe life-threatening reaction, current medical standards for emergency treatment are to be followed.

Symptoms	Action

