Mild Reaction Common • Hyperemia (flushing) • Lightheadedness • Nausea • Mild chest discomfort (tightness) Less Common • Fever and/or shivering • Palpitations • Headache • Irritability (especially in young children)	 Slow infusion rate by 50% Increase infusion time in accordance with institutional standard of care Administer oral anti-pyretic and/or antihistamine Once the event has resolved, the infusion should continue at reduced rate for a minimum of 30 minutes before infusion is increased to 75% of original rate Decrease infusion rate by a further 25% if symptoms persist If symptoms continue despite rate reduction, stop infusion Pre-treat with oral antihistamine and antipyretic prior (approx. 1.5 hours) to next infusion eg, diphenhydramine 25-50 mg by mouth and acetaminophen 650 mg by mouth
 Hyperemia (flushing) Chest discomfort Itching and/or raised urticarial rash Severe headache Gastrointestinal symptoms, vomiting, diarrhea, abdominal cramping 	 Give antihistamine intravenously and consider IV steroids in accordance with institutional standard of care Give any prescribed inhaler treatment if appropriate Collect serum for analysis of tryptase 1-3 hours after the IAR onset and another serum sample for tryptase and ADA during the next study visit (≥4 days after the IAR) prior to the infusion. Pre-treat with oral antihistamine and antipyretic prior to next infusion Skin testing may be considered
 Severe Reaction Clinically significant cardiovascular effects (hypotension defined as a decline approaching 20-30% of their preinfusion value without alternative etiology (agitation, pain, fluid overload, dehydration) Respiratory symptoms: Significant shortness of breath, stridor, wheezing, laryngeal oedema, swelling of tongue. Cardiac arrhythmias Anaphylactic/Anaphylactoid shock with hypotension and circulatory collapse 	 Stop infusion Give oxygen, if available Give intramuscular injection of epinephrine (adrenaline) Give antihistamines intravenously and steroids intravenously Collect serum sample for tryptase 1-3 hours after the IAR onset and another serum sample for tryptase and ADA during the next study visit (≥4 days after the IAR) prior to the infusion. Skin testing may be considered Dosing of the subject will be suspended until the SRC has completed review of the IAR, and any other relevant safety data (Section 6.2)

Table 9:Guidelines for the Management of IARs

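### Section 5.1.7 lets post-infusion vital signs drop to 1 hour from Week 26 of Part C with no condition on dose, so a subject stepped up late from 5 to 10 mg/kg may get the shorter monitoring at first exposure to the doubled dose

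*Protocol*

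**What the plan says.** Protocol Section 5.1.7 sets vital signs about every 15 minutes during the infusion and for 2 hours afterwards. It then permits a shorter period. In Part C the post-infusion period "may be shortened to 1 hour starting with Week 26 of Part C, provided that there is no occurrence of IARs during the infusion". For Part B, the period "may be shortened to 1 hour starting with Week 54, provided that there is no occurrence of IARs during the infusion". The footnotes to the schedules in Appendix D, and to the Weeks 80-104/132-156 table in Appendix C, state 1 hour directly, under the same IAR condition.

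Dose increases stay open beyond those weeks. Section 3.3.3 describes continuing review in Part C to guide "escalation from 5 to 10 mg/kg or reduction from 10 to 5 mg/kg". Section 3.1.3.1 says that the upward step "may not occur without prior written approval from the Sponsor", but it sets no latest week and no monitoring requirement. For Part B, Section 3.3.2 says that "dose escalation may be proposed for individual subject(s) at any time in Part B".

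On reactions, Section 7.1.3 counts a related event as an IAR if it starts during the infusion or within 4 hours of its end. It adds that for similar products "most acute IARs occur within 2 hours of the infusion". Table 9 lists among severe reactions "hypotension defined as a decline approaching 20-30% of their preinfusion value". Under Section 6.2.1 a severe IAR stops that subject's dosing until the Safety Review Committee (SRC) has reviewed it.

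**The concern.** The relaxation suits a subject who has had many uneventful infusions at one dose. It does not suit the first infusion at twice that dose, and the rule does not separate the two. Severe-reaction hypotension is judged against the pre-infusion blood pressure, so finding it depends on a reading being taken. If a fall begins in the second hour after an uneventful infusion, the shortened schedule has no reading to show it, and the stopping rule relies on clinical observation alone.

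The result is also uneven. Two subjects can meet 10 mg/kg for the first time under different monitoring, depending only on whether they were randomised to it or moved to it later. The protocol gives no reason for the difference. Table 2 projects an exposure-based safety margin of 6.1 at 5 mg/kg but only 3.0 or 1.8 at 10 mg/kg, depending on the dose-proportionality assumption.

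**Working it through.** The plan gives no figure to reproduce here. The check sets the rules side by side and makes simple counts.

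**Readings after one infusion** (Section 5.1.7, every 15 minutes)
- 2 hours: 120/15 = 8.
- 1 hour: 60/15 = 4.
- Readings that may be omitted: 8 - 4 = 4.
- Share of the 4-hour post-infusion IAR window covered: 2/4 = 50% against 1/4 = 25%.

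**First exposure to 10 mg/kg, by two routes** (dosing every other week)
- Randomised to 10 mg/kg: 2 hours from Day 0 to Week 24 of Part C, which is 24/2 + 1 = 13 infusions.
- Moved from 5 to 10 mg/kg at Week 26 of Part C or later: possibly no infusion at the new dose with 2 hours.
- Subjects who could take the second route: the 5 randomised to 5 mg/kg (Section 6.7).

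**Does another provision restore the 2 hours?**
- *24-hour in-patient stay.* Section 3.1.3 gives it to the first subject at 5 and the first at 10 mg/kg. The Appendix D note on the Day 1 visit in Part C has the same scope. Section 3.2 is wider and speaks of each subject's first dose, but a later step is not a first Part C dose.
- *Sponsor approval.* It decides whether the dose rises. It does not set how long to monitor.
- *Reset of the visit schedule.* Section 3.2 ties it to entering Part C. Section 6.1 ties it to being dose escalated in Part C, directly after text on starting Part C. No second Day 0 is described.

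**How many Part C infusions fall under the 1-hour rule?** SAP Section 4 gives 90 to 110 weeks in Part C.
- 90 weeks: (90 - 26)/2 + 1 = 33 of 90/2 + 1 = 46, or 72%.
- 110 weeks: (110 - 26)/2 + 1 = 43 of 110/2 + 1 = 56, or 77%.

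These are infusions eligible for shortening. They are not dose increases and do not measure risk.

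**Part B**
- Part C entry runs from Week 156 - 110 = 46 to Week 156 - 90 = 66.
- Section 4.3.4 requires at least 4 doses at 3 mg/kg before Part C. For entry at Week 66 the latest such doses are at Weeks 58, 60, 62 and 64.
- A first 3 mg/kg dose under the 1-hour rule could therefore fall only at Weeks 54, 56 or 58.
- All three weeks are in the Appendix C table whose footnote 1 still says 2 hours without condition.

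**The case against.** A reader might infer that monitoring is cut by the calendar alone. The text does not support that. An infusion with an IAR keeps 2 hours, and Section 5.1.7 permits the shorter period rather than requiring it. The proviso looks only at the infusion itself, however, so it does not help when a reaction begins later. The schedule footnotes also state 1 hour as what will be done.

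The sentence in Section 6.1 is the best contrary text. If being dose escalated in Part C included a later step from 5 to 10 mg/kg, the clock would restart and 2 hours would return. Read with Section 3.2 and with what comes before it, the sentence is about entry to Part C. It does not clearly cover the later step.

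Some of the other side's case stands:
- Late timing is not certain. Section 3.3.3 describes continuing review, and an increase prompted by Week 12 data in Part C would keep 2 hours. An increase that waits for the Week 24 CSF, MRI and neurocognitive results would start at Week 26 at the earliest, when the shorter rule begins.
- The 2-hour remark in Section 7.1.3 does not say whether time runs from the start or the end of the infusion, or how many reactions begin in the second hour afterwards.
- Readings continue every 15 minutes throughout the infusion, and the Sponsor could attach monitoring conditions to its approval.
- Section 3.3.3 justifies lighter Part C safeguards by prior exposure and by the Part A and B safety data. That argument concerns opening each dose level to further subjects. It does not explain why a late step should have less monitoring than a randomised start at the same dose.

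**Conclusion.** The gap is real and minor. Following the rule as written, up to 5 subjects could have about 4 instead of about 8 readings after their first 10 mg/kg infusion. This assumes that the increase comes at Week 26 of Part C or later, that no IAR occurs during that infusion, that the site uses the shorter period, and that the schedule reset means entry to Part C.

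Three larger readings are tempting and fail:
- The 72% to 77% of infusions eligible for shortening is not the size of the problem, because only the first infusion or so after an increase is at issue.
- Part B is not an equal half of it. At most three visits are exposed, and the schedule footnote for those visits still gives 2 hours. This assumes that all 11 subjects enter Part C within the SAP's range; SAP Section 9.3.2 reports all 11 as randomised.
- No reported result is at risk. Adverse event reporting does not follow this schedule, and SAP Sections 5.2.2 and 7.3.3.2 only list vital signs.

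SAP Section 4 records that development stopped in July 2017, so this is a judgement on the plan as written.

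**What to change.** Add one sentence to protocol Section 5.1.7: *After any within-subject dose increase, vital signs are taken for 2 hours after at least the first infusion at the new dose, regardless of study week.*

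Add a cross-reference to it in the six protocol footnotes that state 1 hour: one in Appendix C (Weeks 80-104/132-156) and five in Appendix D.

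Covering a second infusion is optional. Section 3.3.3 offers a loose parallel, since "data from 1 subject who completes the first 2 doses at 5 mg/kg is considered appropriate to initiate dosing at 10 mg/kg", but that is a condition for opening a dose level and not a monitoring period, so the number is a matter of judgement.

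Leave the 2-hour footnote for Weeks 54-78/106-130 in Appendix C as it is. It differs from Section 5.1.7, but a site that follows it complies with both, and aligning it downwards would reduce scheduled monitoring. The copies of the schedules in the SAP appendix need no edit, because no analysis changes.

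The cost is about 1 extra hour and 4 readings per affected infusion. If all five subjects at 5 mg/kg increase once at Week 26 of Part C or later, that is 5 infusions and 5 x 4 = 20 readings. Covering the second infusion as well would make it 10 infusions and 40 readings. A renewed increase after a dose reduction would add to this.
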